1.0 Introduction

1.1 Study Abstract

Preeclampsia occurs in 5-8% of pregnancies and is associated with significant maternal and neonatal morbidity and mortality.¹ Diagnosis of preeclampsia with severe features requires delivery when the diagnosis is made at or beyond 34 weeks gestation. Delivery may be indicated prior to 34 weeks when criteria for expectant management are not met, such as in the setting of uncontrolled maternal hypertension, progression of disease with worsening of laboratory values or persistent clinical symptoms, or worsening fetal well being. Although clear algorithmic guidelines exist for the treatment of acute-onset severe hypertension in the antepartum, intrapartum or postpartum period¹, limited data exists on starting long acting antihypertensive medications to aid in management of elevated blood pressures during induction of labor.

1.2 Primary Aim

To compare Nifedipine 30mg XL with placebo for improved blood pressure control in women with preeclampsia with severe features undergoing induction of labor.

1.3 Primary Hypothesis

Among women with preeclampsia with severe features undergoing induction of labor, Nifedipine 30mg XL decreases need for additional acute antihypertensive treatment compared with placebo.

1.4 Secondary Aims

The secondary aims of this study are to assess the effect of Nifedipine 30mg XL compared with placebo on mode of delivery, indications for cesarean delivery, maternal hypotension and other adverse events, and a composite of maternal and perinatal adverse outcomes.

2.0 Background

Preeclampsia complicates approximately 1 in 25 pregnancies², and is therefore a relatively common obstetric complication. It is the second leading cause of maternal mortality worldwide after hemorrhage, and may lead to maternal comorbidities including stroke, eclampsia, and organ failure. Fetal or neonatal outcomes include intrauterine growth restriction, low birth weight, and stillbirth. Many of the complications associated with preeclampsia lead to early induction of labor or cesarean delivery and subsequent preterm birth.

Preeclampsia with severe features may be diagnosed in the absence of severe blood pressures, defined as systolic blood pressure (SBP) ≥ 160 mm Hg or diastolic blood pressure (DBP) ≥ 110 mm Hg, when other severely defining features are present. These include clinical features (persistent headache or vision disturbances), laboratory features (liver enzymes twice the upper limit of normal, thrombocytopenia with platelet count less than 100,000/mL, or creatinine greater than 1.1mg/dL, or end organ injury). When severe blood pressures are present, prompt management is required to avoid sequelae such as stroke or placental abruption. Existing data support the use of oral Nifedipine or intravenous hydralazine or labetalol for the treatment of hypertensive urgency in pregnancy¹. Optimal treatment for severe blood pressure during induction of labor for the diagnosis of preeclampsia with severe features has not been described, but inadequate blood pressure control is a risk factor for cesarean

delivery. In a review of the Consortium for Safe Labor, at least 27% of women undergoing induction of labor for preeclampsia with severe features between 24-34 weeks gestation required a cesarean delivery for hypertensive disease³. In a review of over 200,000 women using the Prospective database, the frequency of any antihypertensive use in preeclampsia increased between 2006 and 2014, with corresponding risk reduction in stroke⁴.

Acute blood pressure treatment is not without maternal or fetal risk. In about 10% of pregnant patients treated with intravenous labetalol or hydralazine, hypotension (defined as a drop in 30% of SBP) occurs⁵. Rapid and profound decrease in maternal blood pressure may result in hypoperfusion of the uterus secondary to a rightward shift occurring in the pressure autoregulation curve of the uterine arteries⁶, whereas a gradual decrease in blood pressure is safer for both the patient and the fetus, with less risk for maternal dizziness or fetal distress. When a non-reassuring fetal monitoring cannot be adequately resuscitated through maternal volume expansion, repositioning, or improvement in blood pressure, cesarean delivery is indicated.

In the antepartum or postpartum period, the most commonly prescribed oral agents for maintenance therapy include labetalol, methyldopa and Nifedipine. Scant guidelines exist on the introduction of a maintenance or long-acting agent anti-hypertensive medication to control blood pressure during an induction of labor. A recent randomized controlled trial compared oral nifedipine, labetalol and methyldopa in women with severe hypertension, with the primary outcome of non-severe blood pressure at 6 hours after administration of first dose, more common in patients assigned to Nifedipine⁷. In this study, the median time to delivery among all participants was 24 hours, with cesarean delivery for the indication of uncontrolled blood pressure occurring least frequently with Nifedipine (absolute difference of -5.2 compared to labetalol and -3.5 compared to methyldopa).

We propose a randomized double blind placebo controlled trial in women with preeclampsia with severe features undergoing induction of labor, to evaluate the efficacy of Nifedipine XL initiated in the intrapartum period on the need for acute therapy to reduce persistently severe range blood pressure.

2.1 Rationale for a Randomized Controlled Trial

The lack of existing data on optimal hypertension management during induction of labor for preeclampsia with severe features leads to confusion among providers and significant variation in management. Exhausting the algorithms for intravenous labetalol and hydralazine, as well as oral immediate-release nifedipine, necessitates consideration of a continuous infusion of an anti-hypertensive agent, often requiring ICU-level care. Furthermore, intravenous therapy also introduces the risk for cesarean due to non-reassuring fetal status secondary to maternal hypotension. Therefore, patients with persistently severe range blood pressures are at risk for multiple intravenous or immediate-acting oral agents, as well as at risk for cesarean delivery to expedite treatment of preeclampsia.

To further describe best practice management of intrapartum preeclampsia with severe features, we aim to compare long-acting nifedipine 30mg to placebo. This dose will allow full range of options with intravenous labetalol or hydralazine, as well as immediate-release Nifedipine, for the treatment of hypertensive urgency.

3.0 Study Design

This is a randomized double blind placebo controlled trial comparing Nifedipine 30mg XL to placebo in 110 patients after decision has been made to proceed with induction of labor for the diagnosis of preeclampsia with severe features.

Potential study participants will be identified at the time of admission to the labor & delivery unit. Eligibility criteria will be verified. At the time of enrollment, patients will be randomized to either the study drug (oral Nifedipine XL 30mg) or identical placebo. Participants will receive the first dose of the study medication after enrollment unless recorded blood pressure is <120/70. Dosing will continue every 24 hours through delivery. Algorithms for the administration of intravenous labetalol or hydralazine will be utilized by the primary provider at his or her discretion. Postpartum management of hypertension with oral medications will be unblinded and at the provider's discretion.

This study is a randomized, double-blind, placebo controlled single center clinical trial conducted at The Ohio State University Wexner Medical Center, where approximately 216 women are delivered for preeclampsia with severe features each year. These women will be randomized at the time of induction of labor into two groups.

- Oral administration of 30mg Nifedipine XL q24 hours until delivery
- Matching placebo group q24hrs until delivery
- Women may take the study drug/placebo concurrently with intravenous labetalol or hydralazine or immediate release Nifedipine for the treatment of severe blood pressures during cervical ripening and/or induction of labor per unit protocol.
- All other obstetric care will be at the discretion of the primary provider, including but not limited to cervical ripening and augmentation methods, intrapartum resuscitation, IV magnesium for seizure prophylaxis and recommendations regarding mode of delivery. Data will be collected on these components of routine obstetric care. Analysis will be by intent to treat.

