3.4 Study Groups

This study is a randomized, double-blinded placebo controlled single center clinical trial conducted at OSU Wexner Medical Center of 110 women with diagnosis of preeclampsia with severe features. These women will be randomized at the time of admission to the labor & delivery unit to one of two groups:

- Daily Nifedipine 30mg XL
- Identical appearing placebo

Participants in the study will have the study medication administered by their nurse at time of enrollment and randomization, and every 24 hours thereafter until delivery. All other obstetric care will be at the discretion of the primary provider, including but not limited to: treatment of hypertensive urgency, timing and mode of delivery. Data will be collected on these components of routine obstetric care.

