3.7 Randomization Method and Masking

Randomization may occur upon confirmation that all inclusion/exclusion criteria are satisfied, after verification of participant consent and HIPAA authorization.

Consenting women will be randomly assigned to nifedipine 30XL and placebo in a 1:1

ratio according to a randomization sequence prepared by and maintained by independent statistician and available from central investigational pharmacy who will dispense study drug or placebo. The two study arms are double masked; neither the patient nor the clinical staff will be aware of the treatment assignment.

The simple blocked randomization method will be used to generate the randomization sequences because it provides a high probability of balance in treatment assignments, it is unpredictable, and it allows an explicit randomization analysis to be conducted with relative ease.

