4.2 Randomization and Baseline Visit Procedures

Randomization may occur upon confirmation that all inclusion/exclusion criteria are satisfied, after verification of participant consent and HIPAA authorization. Study staff will also verify participant contact information and obtain a Release of Information, as permitted by local policy, to collect outcome and serious adverse event (SAE) documentation. Patients will be assigned next sequential number and central pharmacy will dispense study drug or placebo depending on randomization allocation sequence.

Once the patient is randomized, the patient will receive a study drug or placebo from clinical nurse. She will be instructed to take 1 pill daily until delivery.

In addition to information collected for eligibility, gestational age, and EDC determination, the following information will be obtained at randomization from a patient interview followed by a review of her chart:

- Demographic information: age, race, insurance status
- Medical history: pre-pregnancy weight, current weight, height, chronic disease history
- Obstetrical history including outcomes of all prior pregnancies and which pregnancy(ies) was complicated by preeclampsia.
- Social history: marital status, years of education, alcohol use, tobacco use, and maternal drug use
- Record baseline blood pressure, and baseline preeclampsia laboratory data including platelets, creatinine, liver function tests and proteinuria status, if performed
- Medication use e.g. ASA prior to enrollment, antihypertensive medications including prior administration of acute antihypertensive medications, metformin, anti-platelet agents, etc

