5.0 Sample Size and Power

For the purposes of sample size estimation, it is assumed that 85% of women with diagnosis of preeclampsia with severe features receive acute IV antihypertensive therapy and 74% will require additional IV hypertensive therapy throughout induction of labor process. Assuming rate of additional acute IV antihypertensive (primary outcome) without use of maintenance long acting antihypertensive therapy is 74%. It is estimated that sample size of 110 women is required to demonstrate at least a 40% reduction in use of additional acute antihypertensive therapy with the use of nifedipine 30XL (from 74% to 44%), with a power of 80%, and type I error of 5% 2-sided.

Primary Outcome		Treatment Effect	Power	Total N
Placebo	Nifedipine			
75%	52.5%	30% reduction	80%	140
			85%	160
			90%	188
	45%	40% reduction	80%	82
			85%	92
			90%	108
70%	49%	30% reduction	80%	170
			85%	194
			90%	226
	42%	40% reduction	80%	97
			85%	110
			90%	128
65%	45.5%	30% reduction	80%	202
			85%	230
			90%	270
	39%	40% reduction	80%	114
			85%	130
			90%	150

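### Women are randomized with no blood-pressure condition, yet the first dose depends on one; any woman held is still analysed as allocated, which dilutes the comparison by an unknown, probably modest, amount

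*Combined protocol and SAP*

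**What the plan says.** Section 3.0 (Study Design) gives the order of events. Eligibility is verified, then "At the time of enrollment, patients will be randomized to either the study drug (oral Nifedipine XL 30mg) or identical placebo". The next sentence sets a condition on the tablet: "Participants will receive the first dose of the study medication after enrollment unless recorded blood pressure is <120/70". The same section states "Analysis will be by intent to treat".

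Nothing before allocation carries that condition. Section 3.5 has no lower limit on blood pressure and admits women whether or not they have already had acute treatment. Section 3.7 says "Randomization may occur upon confirmation that all inclusion/exclusion criteria are satisfied", subject to consent and HIPAA authorization, and 4.2 repeats this. Baseline blood pressure is among the items collected at randomization in 4.2, but it is not used to decide whether randomization goes ahead.

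Two other sections describe dosing with no pressure condition. Section 3.4 (quoted up to its last word): "Participants in the study will have the study medication administered by their nurse at time of enrollment and randomization, and every 24 hours thereafter until". Section 4.2: "Once the patient is randomized, the patient will receive a study drug or placebo from clinical nurse".

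**The concern.** As the sections stand, a woman can be eligible, consent, be randomized, and then have the first tablet withheld because of a pressure reading. Intent to treat rightly keeps her in her arm. While she is untreated she cannot show a drug effect, so she moves the two arms' event rates closer together.

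This is plausible in this population. The sample-size section assumes that "85% of women with diagnosis of preeclampsia with severe features receive acute IV antihypertensive therapy", and women may enroll after such treatment, when pressure may be low. The loss is also largely avoidable: the check already exists and baseline pressure is already recorded, so only its place relative to allocation is at issue. After allocation, the loss cannot be undone in the primary analysis without departing from intent to treat.

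A related problem is that 3.0 makes the first dose conditional while 3.4 and 4.2 do not. Until these agree, it is not clear which randomized women would go undosed.

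**Working it through.** **Inputs from the documents.** Placebo rate 74%, nifedipine rate 44%, two-sided type I error 5%, stated power 80%, total 110, so 55 per arm (section 5.0). No allowance for undosed women is stated.

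**The plan's own figure first.** With the pooled-variance normal approximation, 74% versus 44% at 80% power needs 82 women in total, or 96 with a continuity correction. The stated 110 does not reproduce at 80% power; it matches 90% power without correction. This matters here because the headroom in the results below comes from that mismatch, not from a planned allowance.

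**Power with every woman dosed.** Power = Φ{[d√n − 1.96√(2p̄(1−p̄))] / √(p₁(1−p₁) + p₂(1−p₂))}, with n = 55, d = 0.30 and p̄ = 0.59:

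[0.30 × 7.416 − 1.96 × 0.6956] / 0.6624 = 1.30, and Φ(1.30) gives 90.3%.

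**Dilution model.** Let a share h of each arm never be dosed, with the same event rate q in both arms. The rates become 0.74(1−h) + qh and 0.44(1−h) + qh, so the difference is 0.30(1−h). The share h is not in the documents; 3%, 5% and 8.5% are assumptions.

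| h never dosed | Difference | Nifedipine rate if q = 74% | Power, q = 74% | Power, q = 30% | 110 × [1−(1−h)²] |
|---|---|---|---|---|---|
| 0 | 30.0 points | 44.0% | 90.3% | 90.3% | 0 |
| 3% | 29.1 | 44.9% | 88.5% | 88.2% | about 6 women |
| 5% | 28.5 | 45.5% | 87.2% | 86.7% | about 11 |
| 8.5% | 27.45 | 46.6% | 84.7% | 83.7% | about 18 |

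The last column is the approximate equivalent loss of sample size. With q as low as 10%, power at 8.5% is 83.4%.

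**Where 80% is crossed.** Raising h until power at 55 per arm falls to 80% gives 14.2% with q = 74%, 13.0% with q = 50%, 12.4% with q = 25% and 12.1% with q = 10%.

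**Where 8.5% comes from.** It is 85% × 10%. The second factor is the Background statement "In about 10% of pregnant patients treated with intravenous labetalol or hydralazine, hypotension (defined as a drop in 30% of SBP) occurs"; a 30% fall from 160 mmHg gives 160 × 0.7 = 112 mmHg. It is an illustration only, for the reasons given under the objection.

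**Dependence on the test.** The plan names no test for the primary comparison. Fisher's exact test starts lower, at 85.9% with 55 per arm and all dosed. Summing the binomial probabilities of all tables with two-sided Fisher p ≤ 0.05 at the diluted rates for h = 8.5% gives 79.2% (q = 74%) and 77.3% (q = 30%). The crossing point of 12–14% therefore belongs to the pooled normal approximation.

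**The case against.** The strongest case on the other side has five parts.

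- **The text withholds only the first dose.** Section 3.0 does not say that a held woman is never treated, and it goes on to describe dosing every 24 hours. This stands. A reader might infer that some randomized women cannot be dosed at all, but the documents do not say whether a hold is a delay or permanent. The figures above describe the permanent case; a delay would cost less, although events before the delayed dose would still count.
- **The time of the reading is not stated.** The deciding value could be the baseline pressure recorded at randomization in 4.2. This also stands, so it cannot be said that the reading itself follows allocation. What the documents show is that allocation does not depend on it. If the value is already known at that point, using it first adds almost no work.
- **8.5% is not a measured share or an upper limit.** This stands. Neither factor measures pressure below 120/70 at first dose. A woman starting at about 172 mmHg or higher remains at or above 120 after a 30% fall (120 / 0.7 = 171.4). The product ignores the diastolic limb, and it leaves out women diagnosed by the route in section 3.1 that starts at 140/90.
- **There is no bias, and power may still meet the target.** The first part stands: staff and patients are masked, so the hold falls on both arms alike, and the analysis remains a valid estimate of the effect of assignment. The second part holds for the scenarios above under the pooled approximation. It does so because 110 exceeds the 82 to 96 that the plan's inputs require.
- **The change narrows the population and does not remove every hold.** Both parts stand. Pharmacy dispenses after allocation, so pressure may change before the tablet is given, and some women would be randomized later or not at all. Against this, the population would be women who can start treatment, which fits the stated interest in nifedipine initiated intrapartum.

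**Conclusion.** The point holds as a matter of structure. Allocation carries no pressure condition, the first dose does, and intent to treat counts the women in between. The consequence is dilution and lost precision, not bias.

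Its size is unknown. If 3%, 5% or 8.5% were never dosed, power for 74% versus 44% at 55 per arm would go from 90.3% to about 88%, 87% or 83–85%. It passes below the stated 80% only at about 12–14% never dosed. These figures assume the plan's event rates, equal holds in both arms, no drug effect in held women, permanent holds, and the pooled normal approximation; an exact test would leave less room.

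A reader might infer that the trial is underpowered because of the hold. The documents do not support that, since they give no frequency of holds and no statement that any are permanent. The conflict between 3.0 and sections 3.4 and 4.2 is in the text and needs reconciling whatever the size of the dilution. This is a cheap improvement, not a flaw that threatens the result.

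**What to change.** 1. Reconcile 3.0, 3.4 and 4.2 so that they agree on whether the first dose carries a pressure condition, and state when the deciding pressure is read and whether a hold is a delay or permanent. Which clinical rule applies is for the sponsor to settle.
2. In 3.7 and 4.2, place the existing section 3.0 check immediately before randomization, and randomize only when the existing first-dose condition is met. Leave the dosing rule itself unchanged.
3. Keep intent to treat as the primary analysis, and report by arm the number of women whose first dose is still withheld after allocation.

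**Cost.** A short protocol amendment, using a reading that is already recorded at baseline. A few women would be randomized later or not at all, and the population would narrow slightly to women who can start treatment. The effect on recruitment cannot be quantified because the share held is not given.

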3.1 Preeclampsia with severe features diagnosis determination

Among women without a history of chronic hypertension, preeclampsia without severe features is typically made based on elevated blood pressures and proteinuria greater than 300mg/24 urine collection; however, in the absence of proteinuria, the severely-defining features below can be used for diagnostic purposes. Preeclampsia with severe features is diagnosed based on the following:

- Development of hypertension, defined as a persistent SBP of 160mm Hg or higher, or DBP of 110mm Hg or higher on two occasions at least 4 hours apart while the patient is on bedrest (unless antihypertensive therapy is initiated before this time)
- Alternatively, the diagnosis can be made with a SBP of 140 mm Hg or higher, or a DBP of 90 mm Hg or higher after 20 weeks of gestation in a patient with previously normal blood pressure, plus any of the following:
 - Thrombocytopenia, with platelet count of less than 100,000/microliter
 - Impaired liver function as indicated by abnormally elevated blood concentrations of liver enzymes (to twice normal concentration), severe persistent right upper quadrant or epigastric pain unresponsive to medication and not accounted for by alternative diagnoses, or both
 - Progressive renal insufficiency (serum creatinine concentration greater than 1.1mg/dL or a doubling of the serum creatinine concentration in the absence of other renal disease
 - Pulmonary edema
 - New-onset cerebral or visual disturbances

- In women with baseline chronic hypertension, preeclampsia is diagnosed based on any of the following (not accounted for by alternative diagnoses):
 - Severe hypertension (SBP \geq 160 mmHg or DBP \geq 110 mmHg) \geq 20 weeks in gestation on two occasions with measurements taken at least 4 hours apart or 1 occasion with subsequent antihypertensive therapy, or an escalation of antihypertensive medications to control blood pressure
 - New onset of proteinuria or a doubling in protein in women with baseline proteinuria
 - Thrombocytopenia (platelet count $<$ 100,000 per microliter)
 - Progressive renal insufficiency (serum creatinine $>$ 1.1 mg/dl or doubling of the serum creatinine in the absence of other renal disease)
 - Impaired liver function (elevated transaminases \geq 70 U/L, or severe persistent right upper quadrant or epigastric pain unresponsive to medication)
 - Pulmonary edema diagnosed clinically by exam or chest x-ray
 - New-onset and persistent (non-responsive to supportive treatment) cerebral or visual symptoms.
 - HELLP [hemolysis, elevated liver enzymes and low platelet count] syndrome defined as the occurrence of all of the following (not accounted for by alternative diagnoses):
 - Hemolysis: evidenced by (1) serum total bilirubin \geq 1.2 mg/dL (20 μ mol/L), (2) serum lactate dehydrogenase (LDH) \geq 600 IU/L, or (3) hemolysis on peripheral smear
 - Thrombocytopenia (platelet count $<$ 100,000 / microliter)
 - Serum aspartate aminotransferase (AST) or alanine transaminase (ALT) \geq 70 IU/L
- Atypical HELLP defined as the occurrence of 2 of the 3 following (not accounted for by alternative diagnoses)
 - Hemolysis: evidenced by (1) serum total bilirubin \geq 1.2 mg/dL (20 μ mol/L), (2) serum lactate dehydrogenase (LDH) \geq 600 IU/L, or (3) hemolysis on peripheral smear
 - Thrombocytopenia (platelet count $<$ 100,000 / microliter)
 - Serum aspartate aminotransferase (AST) or alanine transaminase (ALT) \geq 70 IU/L

Eclampsia defined as an occurrence of a seizure without any known cause

